1.2 Rationale for the Study

Based on the outcomes of study OVA-301, this non-interventional study will investigate the clinical utility of a platinum-free trabectedin + PLD regimen in patients with progressive ovarian cancer relapsing 6 months or more following the previous platinum-based chemotherapy. This study will assess the value of palliative care by collecting real-life data on the response to trabectedin + PLD, which can be related to the principal objectives of re-treatment for patients with relapsed platinum-sensitive ovarian cancer—to prolong survival, improve quality of life, and alleviate cancer-related symptoms (Poveda et al, 2014).

The aim of this non-interventional, European, multicenter, prospective study is to assess the PFS after trabectedin + PLD therapy for the treatment of relapsed ovarian cancer according to standard local clinical practice following approved SmPC indication and dose, describing patients who were pretreated with an antiangiogenic drug and those not pretreated, in real-life clinical practice.

Patients must have received a minimum of 1 cycle of trabectedin + PLD before their inclusion in the study (Appendix 14.1, Figure 1).

Clinical evidence of PFS, response rate, DCR, survival, treatment parameters, and safety will be obtained in order to evaluate the effectiveness of trabectedin + PLD in patients with relapsed ovarian cancer in Europe.

2 GOALS AND OBJECTIVES

2.1 Primary Objective

To assess the progression-free survival (PFS) according to investigator criteria in relapsed ovarian cancer patients treated with trabectedin + pegylated liposomal doxorubicin (PLD) according to standard local clinical practice following approved Summary of Product Characteristics (SmPC) indication and dose, overall and by previous usage of antiangiogenic drug.

2.2 Secondary Objectives

The secondary objectives will be to determine the following based on real-life clinical data overall and by previous usage of antiangiogenic drug:

- Response rate (CR + PR) and DCR (CR + PR + SD)
- Overall survival (OS)
- Evolution of the patient's performance status (PS)
- Treatment duration and number of cycles, treatment exposure, and time to next treatment
- Safety of the combination of trabectedin + PLD.

Version 4- Amendement 2

3 METHODS

3.1 Study Design Overview

This will be a non-interventional, prospective, multicenter study in which trabectedin + PLD will be administered according to standard local clinical practice following approved SmPC indication and dose. There will be no involvement with any treatment decisions for the patients included in the study. The choice of therapy must be made prior to the patient's inclusion in the study. Treatment administration will be independent of, and dissociated from participation in the study.

For each patient, the study will consist of a Qualification Period (see Section 6.1), an Observation Period (see Section 6.2) and a Follow-up Period (see Section 6.3). Once treatment with trabectedin is discontinued, patients may be treated with subsequent anticancer therapies or supportive care as per the treating clinician's best clinical judgment. The study design is summarized in Appendix 14.1, Figure 1.

3.2 Estimated Duration of the Study

The study will begin with the enrollment of the first patient. The individual patient study duration will be up to 13 months (12-month Observation Period + 1-month Follow-up Period). Enrollment of patients in the study is expected to be completed within 36 months. This target however, is dependent upon the enrollment rate of each individual study center participating in the study. If the targeted enrollment rate of each individual site participating in the study is lower than expected, additional sites may be added.

The total duration of the study will be 49 months, including the 36-month enrollment period and the 13-month study duration of the last patient enrolled in the study.

The planned study periods are as follows:

- Entire study period: September 2014-January 2020
- First patient in: July 2015
- Last patient in: 31 July 2018
- Last patient last visit: August 2019

Given the variation of clinical practice not only across, but also within countries, a good geographical representation of patients with relapsed ovarian cancer will be attempted by targeting study centers spread across the regions of each of the countries. This variation in clinical practices will contribute to more representative results for each country.

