4.2 Number of Patients

At least 300 patients will be selected across approximately 70 European sites. Study sites will be located in Germany, Italy, Spain, France, and Belgium.

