8.3 Detection of Bias

The reason for non-participation in the study (patient declined, no reply, patient not fulfilling the inclusion criteria, or presence of any exclusion criterion) will be recorded in a patient qualification log at each site. This will enable subsequent assessment of potential non-participation (selection) bias necessary for quality assurance of the data collected. Given the variation of clinical practice not only across, but also within countries, a good geographical representation of patients with relapsed ovarian cancer will be attempted

by targeting study centers spread across the regions of each of the countries. This variation in clinical practices will contribute to more representative results for each country as well as across this European region.

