9. STATISTICAL METHODS OF ANALYSIS

9.1 General Principles

All analysis will be based on the FAS and will be presented overall and by previous antiangiogenic usage (yes/no).

Appropriate descriptive statistics will be produced for each parameter. For continuous data the mean, standard deviation, median, minimum and maximum will be presented. For categorical data, the frequency and percentage in each category will be presented. The data will be analyzed using the normal approximation and its 95% CI. However, in analyses where sample size is considered to be too low, the exact binomial estimator and its 95% CI will be calculated. Time-to-event endpoints (PFS and OS) and their fixed-time estimations will be analyzed using the Kaplan-Meier (KM) method.

Any p-values presented will be descriptive in nature and the significance level selected will be 5%.

Statistical analyses will be conducted using SAS version 9.4 or later for Windows, and/or any other applicable software suitable for the planned statistical analyses.

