9.2 Patient Accountability

A summary of the number and percentage of patients enrolled by country and site will be produced.

Data with reasons for non-participation in the study (patient declined, no reply, patient not fulfilling the inclusion criteria, or the presence of any exclusion criterion) collected and recorded in the patient qualification log at each site will be summarized upon data availability.

Patient disposition over the course of the study and summaries for inclusion/exclusion criteria will be provided. The disposition summaries will include the number of patients enrolled, number of patients who did not receive any trabectedin, and the number of patients included in the FAS. The number of trabectedin cycles received before IC was provided and for those patients, time from first dose of trabectedin to IC will be presented.

Reasons for treatment discontinuation will be summarized along with reasons for not completing the study as reported by the investigators.

Survival status at end of study, including number of deaths along with cause of death, will be summarized. Number of deaths along with cause of death within 30 days of last dose of trabectedin will also be presented.

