9.4 Effectiveness Analyses

9.4.1 Analyses of Effectiveness Primary Endpoint

The primary endpoint for this study is PFS. Summaries of the primary endpoint will be based on the FAS. KM estimates and 95% CIs will be calculated based on estimated variance for log-log transformation of the estimate. KM time to event curves will also be presented.

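### The planned 95% intervals for PFS, response and disease control treat patients from about 70 sites as independent; a site-clustered interval should be reported beside them

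*Protocol*

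**What the plan says.** Protocol 4.2 sets the scale: "At least 300 patients will be selected across approximately 70 European sites". "Study sites will be located in Germany, Italy, Spain, France, and Belgium".

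Protocol 3.2 explains why centres are spread over regions. It opens with "Given the variation of clinical practice not only across, but also within countries" and ends with "This variation in clinical practices will contribute to more representative results for each country". SAP 8.3, under the heading Detection of Bias, repeats the argument and extends it: "This variation in clinical practices will contribute to more representative results for each country as well as across this European region".

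Several things that bear on investigator-reported progression and response are left to local judgement:

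- the method and timing of imaging (Protocol 6.2)
- the response criteria, with RECIST 1.1 preferred and others accepted (Protocol 6.2.1)
- dose changes, within the product label (Protocol 5.1)
- continuing treatment despite apparent progression (Protocol 5.1.1)

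For the primary endpoint, SAP 9.4.1 says that Kaplan-Meier "95% CIs will be calculated based on estimated variance for log-log transformation of the estimate". SAP 9.4.2 analyses OS in the same way and gives response rate and disease control rate exact binomial intervals. No planned interval has a site term.

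Outcomes are reported overall and by prior antiangiogenic use (SAP 9.1 and 11). Country and site enter only as an enrolment count: "A summary of the number and percentage of patients enrolled by country and site will be produced" (SAP 9.2).

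**The concern.** The standard log-log Kaplan-Meier and exact binomial intervals are valid when patients are independent. The documents describe a setting in which that may fail. If a centre scans more often than others, or uses its own response criteria, its patients' recorded progression dates and best responses will tend to resemble one another. Each further patient from that centre then adds less information than the standard formula credits, and the interval comes out too short.

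Precision matters here because it is the only reason given for the sample size. Protocol 10.1 and SAP 3.2 say that 300 patients are judged enough to estimate PFS accurately. An interval that overstates precision weakens that one justification.

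A smaller point goes with it. Both documents speak of results for each country, but no output shows an outcome by country, and no country quota or weighting is given. The pooled estimate takes whatever country mix recruitment produces.

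**Working it through.** **The plan's own figure.** The 300 cannot be reproduced, because it comes with no precision target, event count or power. The check therefore starts from the precision that 300 independent patients would give.

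**Inputs from the documents.** N = 300 (a minimum) and about 70 sites (Protocol 4.2), so mean site size m = 300/70 = 4.29. Five countries, with no quota.

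**Assumed inputs.** The ICC (0.01, 0.05, 0.10) and the CV of site size (0 for equal sites, 1 for very uneven sites). The documents give neither.

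**Baseline under independence.** For a proportion near 50%, half-width = 1.96 × √(0.25/300) = 5.7 percentage points. The exact interval is 44.2% to 55.8%. The log-log interval for a PFS probability of 0.50, ignoring censoring, is 0.442 to 0.555.

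**Formulas.**

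- Design effect: DE = 1 + [(1 + CV²) × m − 1] × ICC. For equal sites the multiplier of ICC is 4.29 − 1 = 3.29; for CV 1 it is 2 × 4.29 − 1 = 7.57.
- Widening factor: √DE
- Effective sample size: 300/DE
- True coverage of a nominal 95% interval: 2Φ(1.96/√DE) − 1

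| ICC (assumed) | Site sizes | DE | Interval should be wider by | Effective N | Half-width at 50% (points) | True coverage |
|---|---|---|---|---|---|---|
| 0 | any | 1.00 | 0% | 300 | 5.7 | 95% |
| 0.01 | equal | 1.03 | 1.6% | 290 | 5.75 | 94.6% |
| 0.01 | CV 1 | 1.08 | 3.7% | 279 | 5.9 | 94.1% |
| 0.05 | equal | 1.16 | 7.9% | 258 | 6.1 | 93.1% |
| 0.05 | CV 1 | 1.38 | 17.4% | 218 | 6.6 | 90.5% |
| 0.10 | equal | 1.33 | 15.3% | 226 | 6.5 | 91.1% |
| 0.10 | CV 1 | 1.76 | 32.6% | 171 | 7.5 | 86.1% |

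**On the scale of median PFS (illustration only).** Take the 9.7-month median that Protocol 1.1.3.1 cites for platinum-sensitive patients on the combination in the earlier phase III trial. Assume exponential times and 13 months of follow-up (Protocol 3.2).

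- Expected events = 300 × (1 − 2^(−13/9.7)) ≈ 182.
- Interval = 9.7 × exp(±1.96 × √(DE/182)).
- DE 1: 8.4 to 11.2 months.
- DE 1.16: 8.3 to 11.4 months (computed with DE unrounded).
- DE 1.38: 8.2 to 11.5 months.
- DE 1.76: 8.0 to 11.8 months.

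**By country.** An equal split, which is an assumption, gives 300/5 = 60 patients per country. Half-width at 50% = 1.96 × √(0.25/60) = 12.7 points. With about 36 events, the median interval is roughly 7.0 to 13.4 months, before any allowance for site.

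**The case against.** The strongest objection is that the size of the effect rests wholly on assumed inputs. The documents describe variation in practice; they do not say that outcomes correlate within site. At about four patients per site a low ICC hardly matters, and the worst figures need an ICC of 0.10 and very uneven sites together. More sites may be added under Protocol 3.2, which for a fixed N would lower the mean site size. The design-effect formula is for proportions, so applying it to censored Kaplan-Meier estimates is approximate. The study is descriptive, any p-values are descriptive (SAP 9.1), and no decision rule depends on the width of an interval. All of this stands. It limits the size of the point but does not remove it.

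SAP 8.4 says that method assumptions will be assessed and that other methods may be used. This is relevant, but it names neither independence nor site, and it commits to no alternative.

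Two stronger readings are tempting, and the documents do not support either:

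- A reader might infer that results for each country were promised and then left out. The sentence in Protocol 3.2 and SAP 8.3 explains how centres are chosen. Objectives and endpoints are set overall and by prior antiangiogenic use, and the SAP analyses match them. What remains is a loose phrase with no output behind it.
- A reader might infer that the split by prior antiangiogenic use is partly a split by country. Protocol 4.3.1 ties entry to local label and reimbursement for trabectedin and PLD. Neither document says that access to antiangiogenics differs by country. A cross-tabulation could show it; the text alone cannot.

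**Conclusion.** The point holds as a cheap improvement. The planned intervals assume independence between patients, while the documents themselves give grounds for doubting it within sites. If within-site correlation is positive, the intervals for PFS, response rate and disease control rate are likely too narrow. The shortfall is slight at an ICC of 0.01 and material at 0.05 or above, especially with uneven sites.

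It would be wrong to state as fact that the intervals are too narrow. That needs a positive ICC, which the documents do not give, and at an ICC of zero nothing changes. The figures also assume 300 patients in 70 sites and a design effect borrowed from proportions. The case for scan timing and response criteria does not carry over directly to OS, since death dates do not depend on scans.

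**What to change.** In SAP 9.4.1 and 9.4.2, add a site-clustered 95% interval for overall PFS, response rate and disease control rate, reported next to the standard one. A bootstrap that resamples whole sites, or a robust variance grouped by site, would do. The existing analysis stays as it is. The cost is a little programming on data already collected, and probably a slightly wider second interval.

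For the country wording, choose one of two courses:

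- Add to SAP 11.1 an exploratory table of prior antiangiogenic use, PFS and response rate by country, labelled imprecise (about ±13 points at an assumed 60 patients per country).
- Remove the reference to individual countries from Protocol 3.2 and SAP 8.3. This costs only an edit.

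The country table is optional; the site-clustered interval is the substantive change.

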4 STUDY POPULATION

4.1 General Considerations

The study population will include patients with platinum-sensitive relapsed ovarian cancer who are receiving trabectedin + PLD according to standard local clinical practice following approved SmPC indication and dose.

To be enrolled in this study, the patients must meet all inclusion criteria and have none of the exclusion criteria.

4.2 Number of Patients

At least 300 patients will be selected across approximately 70 European sites. Study sites will be located in Germany, Italy, Spain, France, and Belgium.

4.3 Selection Criteria

If patients meet the selection criteria, they will be invited to participate in the study. Before any study-specific data are recorded, patients will be provided with all the study details prior to their decision to participate and will be requested to sign an informed consent form (ICF) prior to their participation in the study.

4.3.1 Selection Criteria

Patients must comply with all of the following criteria in order to be enrolled into the study:

- Patients must be aged 18 years or older.
- Patients must have platinum-sensitive relapsed ovarian cancer, defined as disease relapse that occurs 6 months or more after completion of last platinum-containing therapy.
- Treatment indication according to local label SmPC and reimbursement for trabectedin and PLD treatment.
- Patients must have received a minimum of 1 cycle of trabectedin + PLD before their inclusion in the study.
- Patients must have signed an informed consent document indicating that they understand the
 purpose and procedures required for the study and are willing to participate in the study.

4.3.2 Failure of Patient Enrollment

The reason(s) for not enrolling a patient in the study (patient declined, no reply, patient not fulfilling the selection criteria) will be recorded in a patient qualification log at each site. This will enable subsequent assessment of potential selection bias necessary for quality assurance of the data collected.

4.4 Discontinuation Criteria

4.4.1 Patient Discontinuation

Patients are free to discontinue the anticancer treatment at any time. Discontinuation of anti-cancer treatment is not considered a study discontinuation and treating clinicians are encouraged to follow the patient as long as possible. Whenever feasible, patients will be followed until death or until end of study.

Patients may request discontinuation from the study at any time. The date and the reason for withdrawal or discontinuation must be recorded in the electronic Case Report Form (eCRF).

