The protocol-defined analysis of OS for OVA-301 did not demonstrate differences across treatment groups: the median OS was 22.2 months for trabectedin + PLD and 18.9 months for PLD (HR = 0.86, P = 0.08). However, a significant imbalance of the platinum-free interval across treatment groups (trabectedin + PLD, mean PFI = 10.6 months; PLD, mean PFI = 13.3 months; P < 0.01) spurred an exploratory multivariate analysis that considered platinum-free interval and other prognostic factors as covariates, which demonstrated a significant OS advantage in favor of trabectedin + PLD (22.6 vs 19.4 months; HR = 0.82, 95% CI: 0.69-0.98). Further analysis with 430 platinum-sensitive patients showed a median OS of 27.0 months for trabectedin + PLD and 24.1 months for PLD (HR = 0.83; 95% CI: 0.67-1.04). For partially platinum-sensitive patients, the median OS of 22.4 months in the trabectedin + PLD group was significantly longer than in the PLD group at 16.4 months (HR = 0.64; 95% CI: 0.47-0.86) (Monk et al, 2012; Poveda et al, 2014).

Further advantages to OS were demonstrated in a subgroup of 94 patients with partially platinum-sensitive disease from the OVA-301 trabectedin + PLD arm who subsequently received platinum-based chemotherapy at progression. Compared with PLD alone, trabectedin + PLD (followed by subsequent platinum-based therapy) induced a 9-month longer median OS (27.7 vs 18.7 months) and a significant 42% decrease in the risk of death (HR = 0.58; P = 0.0153) (Poveda et al, 2014).

Thus, the OVA-301 trial demonstrated a clinical benefit of trabectedin + PLD compared with PLD alone in patients with platinum-sensitive relapsed ovarian cancer.

1.1.3.2 **Safety**

Myelosuppression, elevated alanine aminotransferase (ALT) and aspartate aminotransferase (AST), and fatigue were the primary dose-limiting toxicities in the dose-finding phase I studies.

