6.3 Follow-up Period

A follow-up visit will take place 1 month after the end of the Observation Period. For patients who discontinued trabectedin before 12 months after the Index date, an additional follow-up visit will be performed 12 months after the Index date, except for patients who are dead or have withdrawn consent. Follow-up information may be collected through phone calls with the patient or site visits by the patient.

For each follow-up visit, the following data will be collected, if available:

- Safety assessment (all AEs including ADRs and SADRs). Laboratory tests associated with ADRs and SADRs will be collected when available.
- Reason for discontinuation of treatment with chemotherapy, if applicable. Reason will include the following: treatment completed, PD, toxicity including grade, patient refusal, patient lost to follow-up, withdrawal of consent, inter-current illness of sufficient severity (specify), withdrawal for pregnancy, death (specify the cause), or other (specify).

- Best symptomatic response and best response (except for patients with confirmed PD at discontinuation or who had started a new treatment) and evaluation of treatment duration.
- Survival status.
- Subsequent non-trabectedin anti-cancer treatments that the patient received during the follow-up period, including regimen number, type of therapy, start and stop date, and best response observed for each regimen.

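### Follow-up to death or end of study is stated where feasible, but no survival contact is scheduled beyond 12–13 months from Index, so a median OS is unlikely to be reached and the late OS curve would be unreliable

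*Protocol*

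**What the plan says.** Protocol 4.4.1 treats stopping anticancer treatment as different from leaving the study. It adds that "treating clinicians are encouraged to follow the patient as long as possible" and that "Whenever feasible, patients will be followed until death or until end of study". End of study is not defined.

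The schedule is narrower. Protocol 3.2 states that "The individual patient study duration will be up to 13 months (12-month Observation Period + 1-month Follow-up Period"), and SAP 3.1 repeats this. Protocol 6.3 lists two contacts. The first is general: "A follow-up visit will take place 1 month after the end of the Observation Period". The second is for patients who stop trabectedin before month 12: "an additional follow-up visit will be performed 12 months after the Index date, except for patients who are dead or have withdrawn consent". Nothing later is scheduled, although Protocol 3.2 places last patient last visit in August 2019.

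OS is a secondary endpoint, analysed descriptively in the same way as PFS (Protocol 10.4.4, SAP 9.4.2), with Kaplan-Meier and fixed-time estimates (SAP 9.1) and its own plot (SAP 11.2). Under SAP 5.3 the OS clock starts on Day 1, the first dose. Patients not known to have died are censored at last contact or the last date known alive. Entry requires at least one earlier cycle, with no upper limit (Protocol 4.3.1). Protocol 10.4 assumes non-informative censoring.

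**The concern.** The follow-up wording and the schedule point to different horizons, and OS is the endpoint that depends on which one applies. Three things follow.

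- **Length.** Scheduled contact ends at about half the median OS that the protocol cites for platinum-sensitive patients, so the curve may never fall to 0.5.
- **Who is in the tail.** Time runs from Day 1, but patients enter later. Those with the longest scheduled follow-up from Day 1 enrolled after several cycles, so they were alive and still on treatment at entry.
- **Which late deaths count.** There is no common cut-off. A death that a site happens to hear of at month 20 can enter the analysis, while a survivor with no further contact is censored at month 12–13. Whether late status is known may then depend on the outcome, contrary to the stated censoring assumption.

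The second mechanism pushes the late curve up and the third pushes it down. The documents do not allow the net effect to be sized.

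**Working it through.** **The plan's own figure.** Protocol 3.2 says "The total duration of the study will be 49 months". This reproduces: 36 months of enrolment + 13 months = 49. No event count, precision target or OS assumption supports the 300 patients (Protocol 10.1 refers only to PFS), so there is no OS figure to reproduce.

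**Inputs from the documents.** N = 300; at least one pre-consent cycle; 21-day cycles; 30.4375 days per month (SAP 5.3). Protocol 1.1.3.1 gives median OS on trabectedin + PLD in the cited phase III trial: 22.2 months (all patients), 22.4 (partially platinum-sensitive), and 27.0 (platinum-sensitive: "showed a median OS of 27.0 months for trabectedin + PLD").

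**Assumptions not in the documents.** Exponential survival, S(t) = 0.5^(t/median); no loss to follow-up; uniform accrual; several trial distributions of pre-consent cycles.

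**1. Longest scheduled follow-up from Day 1** = 13 + 21k/30.4375 months for k pre-consent cycles, and survival at that time:

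| k | Follow-up (months) | S, median 27.0 | S, median 22.2 |
|---|---|---|---|
| 1 | 13.7 | 0.70 | 0.65 |
| 2 | 14.4 | 0.69 | 0.64 |
| 6 | 17.1 | 0.64 | 0.59 |

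For scheduled follow-up to equal the median, k would have to be (27.0 − 13) × 30.4375/21 = 20.3 cycles, or (22.2 − 13) × 30.4375/21 = 13.3 cycles.

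**2. Expected deaths.** Under exponential survival the risk after Index does not depend on earlier cycles. Over 13 months from Index:
- median 27.0: 300 × (1 − 0.5^(13/27.0)) = 300 × (1 − 0.716) ≈ 85
- median 22.2: 300 × (1 − 0.5^(13/22.2)) = 300 × (1 − 0.666) ≈ 100

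These are slightly generous, because most early discontinuers have their last planned contact at month 12.

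**3. Chance that at least 150 of 300 have died** by the times in step 1, all patients having that follow-up: about 1e-13 to 2e-7 (median 27.0) and 4e-8 to 0.002 (median 22.2), for k = 1 to 6.

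**4. Kaplan-Meier simulation** (300 patients, 400 runs, log-log intervals, medians 22.2 to 27.0):
- One pre-consent cycle, or 1–6 evenly spread: median never reached.
- A thin late-enrolling tail (geometric up to 12 cycles, or 5% of patients with 10–20): reached in 11–49% of runs, with about 3–7 patients at risk at that point and the upper confidence limit reached in 2% of runs or fewer.

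**5. Twelve-month OS.** S(12) = 0.735 (median 27.0) or 0.688 (median 22.2). The half-width 1.96 × √(S(1 − S)/300) is 0.050 or 0.052, somewhat more once delayed entry is allowed for.

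**6. Status check at last patient last visit.** With "First patient in: July 2015" and uniform entry over 36 months, follow-up from Index runs from 13 to 49 months. Mean survival is (median/ln 2) × [S(13) − S(49)]/36:
- median 27.0: 38.95 × (0.716 − 0.284)/36 = 0.467, so about 160 deaths
- median 22.2: 32.03 × (0.666 − 0.217)/36 = 0.400, so about 180 deaths

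In simulation (entry over about 37 months) the median was reached in every run. With one pre-consent cycle it was 27.6 months (95% CI about 23–33) for a true 27.0, and 22.9 (about 19–27) for a true 22.2.

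**7. Delayed entry.** With 1–6 pre-consent cycles, ordinary Kaplan-Meier under the same status check gave 29.3 for a true 27.0 and 24.4 for a true 22.2, about 2 months too high. The mean time before entry is 3.5 × 21/30.4375 = 2.4 months, which accounts for it.

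**The case against.** The case for leaving this alone is substantial, and much of it stands.

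- A reader might infer that the protocol promises follow-up to death. It does not: Protocol 4.4.1 says whenever feasible and only encourages clinicians. Because end of study is undefined, it could mean the patient's own month 12–13, and then nothing conflicts. That is an ambiguity to remove, since sites can read it either way.
- A reader might infer that median OS cannot be estimated. That is too strong. Pre-consent cycles have no upper limit, unscheduled contacts count under the last-known-alive rule, and the result depends on the assumed median. Neither document names median OS as a target, and fixed-time estimates are already planned.
- The 27.0 months is background from a randomised trial and is not set as a benchmark. The same section gives 22.2 and 22.4, hence the range used here.
- A reader might infer that only patients still on trabectedin at month 12 are contacted between months 12 and 13. Patients who stop in months 11–12 also have their one-month visit then.
- The survival time left uncollected is not years for everyone. A July 2015 entrant reaches month 13 in August 2016, 36 months before August 2019. A December 2017 entrant reaches it in January 2019, 7 months before.
- OS is secondary and descriptive, and a longer follow-up is not free.

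What remains unanswered is the open censoring date, the selected tail and the absence of any delayed-entry method. The plan would print a full OS curve without a rule for where it stops being interpretable.

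**Conclusion.** The point holds in limited form. The follow-up stated in Protocol 4.4.1 has no schedule behind it after 12–13 months from Index. If OS is like that of the cited trial (22.2 to 27.0 months), survival is about 0.59–0.70 when scheduled contact from Day 1 ends, for 1–6 pre-consent cycles, with about 85–100 deaths in 300. A Kaplan-Meier median is then unlikely to be reached, and would rest on a handful of patients if it were. Beyond about 13–14 months from Day 1 the curve depends on late enrollers and incidental contacts, and late deaths can be captured selectively.

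This rests on exponential survival, an OS median borrowed from the cited trial and assumed pre-consent cycles. Markedly shorter survival in practice would weaken it: with one prior cycle, the true median would have to be about 14 months or less for scheduled follow-up to reach it. Twelve-month OS is estimable to about ±0.05. A reader might extend the point to the primary endpoint; nothing in this argument undermines PFS. The matter should be settled before database lock.

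**What to change.** Choose one of two routes.

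**(a) Wording and analysis only.** Define end of study in Protocol 4.4.1 consistently with 3.2 and 6.3. In SAP 5.3 and 9.4.2, limit OS to fixed-time estimates up to 12 months from Day 1, censor administratively there, and show numbers at risk. Every surviving, non-withdrawn patient is due a contact at 12 months after Index or later, which lies beyond 12 months from Day 1, so scheduled follow-up covers this horizon. The cost is a less ambitious OS claim.

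**(b) Give effect to 4.4.1.** Add to Protocol 6.3 one survival-status update for every non-withdrawn patient at last patient last visit (August 2019), with a common censoring date in SAP 5.3. Protocol 6.3 already accepts telephone contact; it does not mention chart review. Expected deaths rise to about 160–180. The cost is a protocol amendment with ethics approval (Protocol 11.5) and a brief contact per patient across about 70 sites before the November 2019 lock. Whether the existing consent covers this contact should be confirmed.

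**Under either route**, analyse OS with delayed entry: time since Day 1, with each patient joining the risk set at enrolment (left truncation), and early numbers at risk shown. Without this, the median under (b) stays about 2 months too high with 1–6 pre-consent cycles. Left truncation removes the guaranteed survival before entry. It does not remove selection of patients who were still on treatment at entry, so the report should state that limit. The cost is programming only.
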